8.4.3 UNANTICIPATED PROBLEM REPORTING

Study personnel will report all incidents or events that meet the criteria for unanticipated problems immediately to the PIs. The PIs will then report the unanticipated problem to the local IRB, the Safety Monitor and the study sponsor (see below).

Unanticipated problems that are serious adverse events will be reported to the IRB and to the study sponsor within 72 hours of the PIs becoming aware of the event.

If the unanticipated problem results in a subject's death or is life-threatening, it will be reported by the PIs to the local IRB and the study sponsor (see below) within 24 hours of the PI's knowledge of the event.

After initial notification, a written report will be submitted to the IRB, the Safety Monitor and the study sponsor within 7 calendar days of initial notification. In addition to a description of the event, the report

will include an explanation of the basis for determining that the event represents an unanticipated problem and a description of any changes to the protocol or other corrective actions that have been taken or are proposed in response to the unanticipated problem.

Any other anticipated problems that do not involve risks to subjects or others will be reported to the IRB and to the study sponsor on an annual basis, as part of the annual IRB review of the protocol.

Reporting to study sponsor

All unanticipated problems involving risk to subjects or others will be promptly reported by [contact]), by email ([contact]), or by [contact]) to the USAMRMC, Office of Research Protections, Human Research Protection Office. A complete written report will follow the initial notification. In addition to the methods above, the complete report will be sent to the U.S. Army Medical Research and Materiel Command, ATTN: MCMR-ZB-PH, [name].

8.4.4 EVENTS OF SPECIAL INTEREST

N/A

8.4.5 REPORTING OF PREGNANCY

N/A

8.5 STUDY HALTING RULES

Administration of the study device will be halted immediately if there is a serious adverse event or a serious unanticipated problem. The PIs will notify the local IRB, the Safety Monitor and the study sponsor within 24 hours.

8.6 SAFETY OVERSIGHT

Safety oversight will be under the direction of an independent Research Safety Monitor ([name]). [name] is totally independent from the study, does not have any conflicts of interest, and has expertise relevant to the duties he will perform as the Research Safety Monitor (see biosketch uploaded in IRBnet). The study team will send reports to the Safety Monitor addressing recruitment, withdrawals, adverse event reports and interim analyses (when performed). The Safety Monitor will provide an annual report to the local IRB and the USAMRMC, Office of Research Protections, Human Research Protection Office as part of the annual IRB review of the protocol. If there are any urgent concerns, the Safety Monitor will immediately contact the local IRB and the USAMRMC, Office of Research Protections, Human Research Protection Office. The Safety Monitor will have authority to stop the research protocol in progress, remove individual human subjects from the research protocol, and take whatever steps are necessary to protect the safety and well-being of human subjects until the local IRB can assess his report.

9 CLINICAL MONITORING

Monitoring will be conducted by the PIs to ensure that the rights and well-being of human subjects are protected, that the reported trial data are accurate, complete, and verifiable, and that the conduct of the trial is in compliance with the currently approved protocol/amendment(s), with GCP, and with applicable regulatory requirement(s). Please also see section 12.

10 STATISTICAL CONSIDERATIONS

10.1 STATISTICAL AND ANALYTICAL PLANS

There will not be a formal SAP.

10.2 STATISTICAL HYPOTHESES

Primary efficacy endpoint

The primary outcome measure will be the number of collision incidents (all contacts) in the active and silent modes. Fewer collision incidents during the active warning mode than the silent mode will indicate an effective intervention. This analysis will include data collected throughout all of the period of home-use of the device.

Since subjects will likely use the device for differing amounts of time and are exposed to different number of hazards, the number of collisions will be expressed as the rate of collisions for analyses.

Null hypothesis: There will be no difference in the rate of collisions between the active and silent modes

Alternative hypothesis: There will be a difference in the rate of collisions between the active and silent modes

10.3 ANALYSIS DATASETS

The dataset for the analysis of the primary efficacy outcome measure will be a modified intention-to-treat dataset. Only participants who have completed the home-use part of the study will be included in the analysis.

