5.4 PARTICIPANT WITHDRAWAL OR TERMINATION

5.4.1 REASONS FOR WITHDRAWAL OR TERMINATION

Participants are free to withdraw from participation in the study at any time upon request.

An investigator may terminate participation in the study if:

- A participant is not using the device correctly or appears to be engaging in risky behaviors when using the device.
- The participant meets an exclusion criterion (either newly developed or not previously recognized) that precludes further study participation.
- Any other situation occurs such that continued participation in the study would not be in the best interest of the participant

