7.3.5 EARLY TERMINATION VISIT

An experimenter will be checking in with subjects approximately once every week when they are using the device at home to check on their progress with the device. Any subject that is not using the device correctly or appears to be engaging in risky behaviors when using the device will be terminated early. If at any point subjects experience difficulty and wish to withdraw from the study they can notify the experimenter and discontinue participation. They will be asked to return the device and, if willing, complete a questionnaire about their experience with the device.

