10.4.5 ADHERENCE AND RETENTION ANALYSES

The amount that the collision warning device is used each day will be recorded by the device and will be summarized with descriptive statistics. The number of participants who withdraw from the study after visit 1, after visit 2, and after starting to use the device at home will be recorded and summarized with descriptive statistics.

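### Section 10.3 labels the primary efficacy set modified intention-to-treat, but its rule makes it a completers set, and no inferential efficacy analysis explicitly includes people who leave during home use

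*Combined protocol and SAP*

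**What the plan says.** Section 10.3 is two sentences long. The first states that the primary efficacy dataset "will be a modified intention-to-treat dataset". The second is the only inclusion rule: "Only participants who have completed the home-use part of the study will be included in the analysis". It sets no minimum amount of data and does not require data in both modes.

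Participants can leave after dispensing in several ways. Section 5.4.1 lets an investigator end participation on this ground: "A participant is not using the device correctly or appears to be engaging in risky behaviors when using the device". Section 7.3.5 is firmer, saying that anyone "not using the device correctly or appears to be engaging in risky behaviors when using the device will be terminated early". It also covers voluntary exit: "If at any point subjects experience difficulty and wish to withdraw from the study they can notify the experimenter and discontinue participation". Section 10.4.5 expects exits at this stage, since it counts withdrawals "after visit 1, after visit 2, and after starting to use the device at home".

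Section 10.1 adds: "There will not be a formal SAP". Section 10.3 is therefore the only place where the analysis set is fixed.

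**The concern.** A reader who sees modified intention-to-treat expects nearly everyone who started the intervention to be analysed, with a few exclusions on stated grounds. The rule in 10.3 instead conditions on finishing. The exits named in 5.4.1 and 7.3.5 concern how a person gets on with the device, so they are plausibly related to how much the person benefits.

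At stake is what the headline percentage reduction means. The stated aim is efficacy in the actual operational environment. Under 10.3 the estimate describes people who finished home use, not everyone who took the device home, and the plan has no analysis that would show whether the two differ. Section 5.4.2 provides for extra recruitment if withdrawals exceed expectation. That restores the number of participants but does not bring back the kind of participant who left.

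**Working it through.** The plan gives no figure for exits after dispensing, so most of this check sets the sections side by side.

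**1. Label against rule.** Completion of home use is the whole criterion in 10.3. The statement in 10.2 that data from the entire home-use period will be used concerns the time span. It does not readmit people whom 10.3 excludes.

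**2. Is there another analysis that includes leavers?**

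| Section | Content | Leavers included? |
|---|---|---|
| 10.4.2 | Primary Wilcoxon test and regression model | No, by 10.3 |
| 10.4.3 | Body contacts, by the primary methods | No set named |
| 10.4.4 | Collisions by mode, descriptive | Not restricted, no set named |
| 10.4.5 | Device use and withdrawal counts, descriptive | Withdrawals counted |
| 10.4.11 | Exploratory study of collision incidents | Not restricted, no set named |

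No inferential efficacy analysis explicitly includes them. Descriptive summaries may.

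**3. Is completion defined?** No. The Schematic of Study Design lets home use end before Day 28 when data accumulate quickly, and section 7.1.1 allows alternatives to attending Visit 4. The line between an early completer and an early leaver is left open.

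**4. Could partial data be analysed?** Section 10.2 already expects unequal exposure: "Since subjects will likely use the device for differing amounts of time". Section 10.4.2 plans duration of use and number of true hazards as offsets in a within-subject model. A shorter record fits that model without new methods, provided both modes were recorded. Section 10.6.1 does not say how often the modes switch, so the number of leavers with both modes is unknown.

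**5. How many people could this be?** From section 10.5, the total is 42, the evaluable target is 31 and attrition is 30%. Then 42 − 31 = 11, and 42 × 0.30 = 12.6. The number lost after dispensing can therefore lie anywhere from 0 to about 13. The upper end would need every loss to fall after dispensing.

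**6. Direction.** With equal weight per person, n_C completers with mean effect d_C and n_L leavers with mean effect d_L, the mean effect in all dispensed is (n_C·d_C + n_L·d_L)/(n_C + n_L). The completers' figure exceeds this by n_L·(d_C − d_L)/(n_C + n_L). The gap is zero if nobody leaves or if d_L = d_C, positive if leavers benefit less, and negative if they benefit more. The documents give neither n_L nor d_L.

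**7. Why short exposures need care in the Wilcoxon test.** The rate is contacts per 100 true hazards per hour. Take 10 contacts per 100 hazards (illustrative). Over 20 hours the rate is 10/20 = 0.5; over 1 hour it is 10/1 = 10. The contact risk per hazard is the same, but the rate is 20 times larger. With T hours in each mode, the within-person difference in rates is the difference in contacts per 100 hazards divided by T, so short records could take the largest ranks. In a rate ratio the T cancels when hours are equal in the two modes, though not when they differ.

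**The case against.** The strongest reply has four parts.

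- **The design protects the comparison.** Each participant supplies both modes, so dropping leavers does not unbalance active against silent among those analysed. This stands. A reader might infer that the primary test is invalid or biased toward the device; the documents support neither.
- **Not all data from leavers are discarded.** A reader might infer from 10.3 that leavers vanish from the trial altogether. That goes too far: 10.3 governs the primary efficacy measure, and the summaries in 10.4.4, 10.4.5 and 10.4.11 carry no completer restriction. What remains is the absence of an inferential analysis that includes them.
- **Few may leave.** A specialist decides before dispensing whether each person may take the device home, and weekly calls follow. Losses can also come earlier: only four devices exist, there is a waiting list, and up to a year may pass between Visits 1 and 3. Reading the full 30% as home-use dropout is therefore unsupported. This limits the weight of the point but does not answer it, because the plan expects some exits after dispensing.
- **An all-exposed primary test could be worse.** Short exposures inflate differences on the planned rate scale, and records from people terminated for incorrect use may be hard to interpret. This stands as a reason not to replace the completers set outright in the Wilcoxon test. It does not argue against a second, pre-specified analysis with the planned model.

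**Conclusion.** The point holds and should be fixed. The label and the rule in 10.3 disagree, completion is undefined, and people who leave after dispensing are in no explicit inferential efficacy analysis even when they have data in both modes. The contrast among completers is valid, but the percentage reduction applies to completers only.

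Confidence is high on what the text says. There is no basis in the documents for a size or a direction of selection, and none is claimed. The point would have no numerical consequence if nobody left after dispensing, or if leavers' effect matched completers'. That leaving is related to benefit is an inference from the exit reasons in 5.4.1 and 7.3.5, not something the documents state.

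**What to change.** In section 10.3:

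1. Call the present set a completers set, and define completion before unmasking, for example as reaching Visit 4 or its permitted alternative.
2. Add a pre-specified efficacy analysis of all participants dispensed the device who have home-use exposure in both modes. Use all data up to withdrawal or termination, in the within-subject negative binomial mixed model with the offsets planned in 10.4.2.
3. Report this beside the completers result, and list exits after dispensing by reason and by whether both modes were recorded.
4. If the wider set is also used for the Wilcoxon test, fix a minimum exposure per mode (hours and reviewed true hazards) before unmasking. The home-use pilot described in 2.1 could inform the value.

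None of this alters the rules for ending participation.

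The cost is protocol wording and review of extra clips that leavers' devices have already recorded. The downsides are noisier data from short exposures, some remaining selection through the both-modes requirement and any minimum-exposure rule, and a possibly smaller estimate if leavers benefit less.

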10.4 DESCRIPTION OF STATISTICAL METHODS

10.4.1 GENERAL APPROACH

This phase 3 clinical trial will use a prospective, double-masked, controlled within-subjects design. Descriptive statistics for continuous data for each of the primary and secondary endpoints will be presented as means with standard deviations or medians and ranges, as appropriate. The normality of the data will be examined and appropriate statistics and descriptives used based on the results. For inferential statistics, an alpha level of 0.05 will be taken to indicate statistical significance with correction for multiple comparisons when necessary.

10.4.2 ANALYSIS OF THE PRIMARY EFFICACY ENDPOINT(S)

The analysis will start with descriptive and graphical summaries of the rate of collision incidents (all contacts) in the active and silent modes, and the difference between active and silent modes. The rate will be computed as the rate of contacts per 100 true hazards (reviewed) per hour. The rate computation takes account of both duration of use and number of true hazards encountered, since some subjects might walk for longer but encounter fewer hazards while others might encounter more hazards in a shorter duration. Contacts will include all contacts with the collision hazard, either with their mobility aids (such as long cane) or body (touching with hand, bumping into the obstacle).

The primary analysis will start by comparing the within-subject difference in the rate of collisions (all contacts) between the active and silent modes using a Wilcoxon Signed-Rank test.

Next a model will be constructed to evaluate within-subject differences in the rates of collisions taking account of other factors that might affect the primary outcome measure. Since the number of contacts will represent overinflated count data, negative binomial regression models – considered to be more appropriate than Poisson regression models for such distributions – will be used for evaluating the association between rate of contacts and device operating condition (active vs. silent). In actual implementation of the regression model, the outcome will be set as the number of contacts (all contacts), while the exposure variable consisting of the duration of device use and the number of true hazards will be the offsets, and the estimated regression coefficients will be expressed as the rate ratio (β). The role of other possible predictors that could potentially affect the rate of contacts will be analyzed. These predictors will be taken from four broad categories: device data, demographics, vision characteristics, and mobility characteristics. Each predictor will be evaluated individually in a generalized mixed effects modeling framework (because we want to estimate within-subject effects) that will also include device condition. Any significant predictors ($p < 0.05$) and possible confounders (causing $\geq 10\%$ change in the rate ratio for the device condition predictor) will be selected for inclusion in the final model to determine the effect of device condition on rate of contacts.

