4.2 STUDY ENDPOINTS

4.2.1 PRIMARY ENDPOINT

The primary outcome measure will be the difference in the number of collision incidents (all contacts) in the active and silent modes. Fewer collision incidents during the active warning mode than the silent mode will indicate an effective intervention; the intervention benefit will be quantified by the percentage reduction in collision incidents (all contacts).

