10.4.3 ANALYSIS OF THE SECONDARY ENDPOINT(S)

Analysis of the secondary measure, number of body contacts will follow that same methods as described for the primary measure, number of collisions (all contacts). Number of body contacts will be expressed as the rate of body contacts per 100 true hazards per hour.

Rating scale responses from the device questionnaire will be summarized using descriptive statistics. Responses to open-ended questions will be examined for common themes and coded accordingly.

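### The primary rate divides contacts by both true hazards and hours, which shifts weight in the signed-rank test to participants with least use and costs some power compared with contacts per hazard

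*Combined protocol and SAP*

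**What the plan says.** Section 10.2 explains why a rate is used: "Since subjects will likely use the device for differing amounts of time and are exposed to different number of hazards". Section 10.4.2 then fixes the definition: "The rate will be computed as the rate of contacts per 100 true hazards (reviewed) per hour". It justifies using both divisors on the ground that "some subjects might walk for longer but encounter fewer hazards while others might encounter more hazards in a shorter duration". The numerator is tied to the hazards: "Contacts will include all contacts with the collision hazard", whether made with a mobility aid or the body.

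The primary comparison begins with a Wilcoxon signed-rank test on the within-subject difference in this rate. A negative binomial model follows, in which "the exposure variable consisting of the duration of device use and the number of true hazards will be the offsets". The model clause confirms that both quantities act as divisors. Section 10.4.3 carries the rate over to the secondary endpoint: "Number of body contacts will be expressed as the rate of body contacts per 100 true hazards per hour". Section 4.2.1 expresses the benefit as a percentage reduction but does not say how it is aggregated across participants.

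Section 10.6.1 says that each participant gets a different randomized active/silent schedule. It gives neither the share of time in each mode nor the switching interval. No section gives expected hours, their spread or the hazard density. Section 10.1 says there will be no formal SAP, so these sections are the whole specification.

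**The concern.** Someone who walks longer meets more hazards, so the hazard count already contains duration. Dividing by hours as well makes the outcome depend on how long a person used the device, even when the risk at each hazard is unchanged. The result is neither a risk per hazard nor a number of contacts per hour.

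The Wilcoxon test ranks differences across participants. A divisor that varies between participants therefore changes who drives the result, and here it favors those who contribute least data. At stake are power, the clarity of the primary quantity, and possibly the precision of the percentage reduction. The same applies to body contacts.

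**Working it through.** **The plan's sample size.** Section 10.5 assumes a paired difference of 0.2 with SD 0.38, alpha 0.05 and power 0.8. The standardized effect is 0.2/0.38 = 0.526. A two-sided paired t-test needs 30.3, so 31 participants, which matches the plan. This figure comes from an obstacle-course difference, not from contacts per hazard per hour, so it does not settle the present question.

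**Algebra (no assumed inputs beyond contacts arising at hazards).** Let p be the contact risk per hazard, H the hazards met, T the hours and C the contacts.
- Expected C = pH, so 100C/H = 100p and 100C/(HT) = 100p/T.
- With offsets log H and log T, both with coefficient 1, the model takes expected contacts as proportional to H × T. If both double, it expects 2 × 2 = 4 times the contacts, while C = pH gives 2 times.
- The sponsor's own example: suppose two people each meet 100 hazards at p = 0.2, one in 5 h and the other in 20 h. Contacts per 100 hazards are 20 for both. The planned rate is 20/5 = 4.0 and 20/20 = 1.0. The per-hazard rate already handles different walking times; the second division creates a difference.

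**Weighting with equal mode hours.** Two participants each drop from 20 to 15 contacts per 100 hazards. At 2.5 h per mode the planned difference is (20 − 15)/2.5 = 2.0. At 20 h per mode it is (20 − 15)/20 = 0.25. Per hazard, both are 5. The test uses ranks, so this is not eightfold weight. In simulation with equal mode hours, the lowest-use third held 43–44% of the rank sum under the planned rate and 34–36% per hazard.

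**Power of the signed-rank test (simulated).** Taken from the plan: n = 31, two-sided 0.05. Assumed: total hours log-normal with median 20, split equally between modes; hazards per hour log-normal with median 6 and log-SD 0.5, varying between modes with CV 0.3; contact risk 0.2 (logit SD 0.5); beta-binomial contacts with intraclass correlation 0.05; a true 25% reduction. Simulation error is about 0.01 to 0.015.

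| Log-SD of hours | Per hazard | Planned rate | Loss (points) |
|---|---|---|---|
| 0.2 | 0.48 | 0.47 | 1 |
| 0.3 | 0.47 | 0.45 | 2 |
| 0.5 | 0.48 | 0.44 | 4 |
| 0.8 | 0.50 | 0.43 | 7 |

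Allowing hazard density to be equal between modes, or removing overdispersion, gives ranges of about 0–3, 4–5 and 7–10 points at log-SD 0.2–0.3, 0.5 and 0.8.

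A second set of assumptions (median 5 h per mode, 10 hazards per hour, 15% risk, negative binomial dispersion 0.3, rate ratio 0.51) shows the effect of mode hours that differ at random within a participant. At log-SD 0.4, power is 87% against 84% with equal mode hours and 86% against 78% with a random split (logit SD 0.4). At log-SD 0.8 it is 83% against 76%, and 84% against 69%.

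**Validity.** With no device effect and equal hours, type I error is near 5%. Within a participant, the active/silent ratio is multiplied by silent hours/active hours: 45/55 = 0.82 and 40/60 = 0.67. If every participant had a fixed 55:45 active:silent split, the rejection rate would be 26% on the first set of assumptions and 12% on the second. At 60:40 it would be 72% and 37%. Contacts per hazard stays near 5%.

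**Regression.** With subject effects, hours common to both modes cancel. Simulated power with the hazards offset alone against both offsets is 0.53 and 0.53 (equal hours), 0.52 and 0.52 (1-hour blocks in balanced pairs), and 0.51 and 0.50 (independent 5-minute blocks). These runs used fixed subject effects; the plan specifies mixed effects.

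**Percentage reduction.** As a ratio of mean rates, its SD is 13.8 points under the planned rate and 11.0 per hazard. As a median of individual reductions with equal hours, T cancels and the SD is 14.0 under both.

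**The case against.** The sponsor gives a reason for using both divisors, and the test keeps its level when mode hours balance. If use varies little between participants, the power loss is about zero. Every input on hours, hazards and risk is assumed. The regression, which the plan uses to determine the device effect after adjustment, is nearly untouched. The planned rate can even beat contacts per hour: 0.43–0.45 against 0.35–0.39 under overdispersion, CV 0.3 and a 20 h median, with mode hours equal or nearly so. When contacts were generated in proportion to hazards × hours, as the plan's model supposes, contacts per hazard did as well or slightly better (83% against 80%, 77% against 77%). One setting, with a much larger benefit in low-use participants, reversed the order slightly (69% against 70%).

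Most of this stands and limits the size of the point. It does not remove it: the stated reason is already met by contacts per hazard, and the loss of power appears in nearly all settings tried.

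A reader might infer three stronger things that the documents do not support:
- **That the primary test is biased.** This would need systematically unequal mode hours. The schedule is randomized and the split is not stated, so no existing bias can be claimed.
- **That the power loss is large.** Large losses need mode hours that differ clearly within participants, under a schedule the documents do not describe.
- **That the regression and the percentage reduction always suffer.** The first does so only with clearly unequal mode hours. The second depends on an estimator the plan does not name.

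**Conclusion.** The point holds for the weighting in the signed-rank test and for interpretability. At constant risk per hazard the planned rate is 100p/T, so it falls with use, and participants with least data gain rank weight (about 44% against about 35% for the lowest-use third, on assumed inputs). The direction of the power loss is well supported. Its size cannot be fixed from the documents and runs from about zero to roughly 10 points over the spreads of hours examined, with more if hours also differ between modes. The plan itself expects overdispersion ("the number of contacts will represent overinflated count data"), and under it the loss was 7 points at log-SD 0.8.

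Validity is not in question if mode hours balance. Contacts per hazard has the further advantage of not depending on that balance. This is worth correcting, but it does not by itself undermine the trial.

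**What to change.** Before the mode code is broken, amend sections 10.4.2 and 10.4.3 as follows:
- Make contacts, and body contacts, per 100 reviewed true hazards the rate for the signed-rank test.
- Use log(true hazards) as the only offset in the negative binomial model.
- Report contacts per hour, with log(hours) as the only offset, as a sensitivity analysis.
- State that the percentage reduction is computed from the primary rate, and how it is aggregated across participants.
- State the intended active/silent split and switching interval, and report hours and true hazards by mode.

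The cost is protocol wording and analysis code; no new data are needed. One downside should be stated: a rate per hazard gives no credit if the device helps people meet fewer hazards. The planned rate gives none either, and the per-hour sensitivity analysis would show it.

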10.4.9 MULTIPLE COMPARISON/MULTIPLICITY

Correction for multiple comparisons will be used when appropriate.

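### Section 10.4.2 does not say whether the Wilcoxon test or a predictor-screened model decides the primary endpoint, and the screening can adjust away part of the device effect

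*Combined protocol and SAP*

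**What the plan says.** Section 10.4.2 describes the analysis in sequence. "The primary analysis will start by comparing the within-subject difference in the rate of collisions", using a Wilcoxon signed-rank test. A negative binomial model follows, in a mixed-effects framework, with duration of use and number of true hazards as offsets.

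Other factors are then considered. "These predictors will be taken from four broad categories: device data, demographics, vision characteristics, and mobility characteristics"; no variable is listed under any of them. Each is tried singly alongside device condition. Those with p < 0.05, and those that change the device rate ratio by at least 10%, "will be selected for inclusion in the final model to determine the effect of device condition on rate of contacts".

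Section 4.2.1 expresses the benefit as a percentage reduction in collision incidents. Section 10.4.3 carries the approach over to the secondary endpoint: "number of body contacts will follow that same methods as described for the primary measure".

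On error control, Section 10.4.1 sets alpha at 0.05 "with correction for multiple comparisons when necessary", and Section 10.4.9 says only "Correction for multiple comparisons will be used when appropriate". Section 10.1 states "There will not be a formal SAP". Section 10.2 gives one null hypothesis and names no test.

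**The concern.** There are two linked problems.

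**No ranking.** Calling the Wilcoxon test the start of the primary analysis points to that test. Giving the final model the job of determining the device effect points to the model. If one is significant and the other is not, the plan has no pre-stated conclusion, and with no SAP there is no later document to settle it.

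**The screening suits this design poorly.** Mode is randomised within subject (Section 10.6.1). Demographics, vision and baseline mobility are the same for a subject in both modes. A variable that moves the device rate ratio materially must therefore differ between modes, which means it was recorded during home use. The warnings may have changed it. Walking speed and activity level, named as exploratory factors in Section 10.4.11, would be examples if they are among the device data and measured per mode. Adjusting for such a variable removes part of the effect under test. A signed-rank test gives no percentage reduction, so the final model's rate ratio is the model-based estimate a reader would take up.

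**Working it through.** **1. The plan's own figure.** Section 10.5 gives a difference of 0.2, SD of change 0.38, alpha 0.05 and power 0.8. The alternative in Section 10.2 is non-directional, so the test is two-sided. The standardised difference is 0.2/0.38 = 0.526. A paired t-test needs n = 30.3, so 31, as stated; power is 0.796 at 30 and 0.809 at 31. The sizing is a plain paired comparison with no covariates.

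**2. Which variables can move the device effect.** Write the log rate for subject i in mode m as a_i + b·m + g·x_im. The active-minus-silent difference is b + g·Δx_i. For a baseline variable Δx_i = 0, so it drops out. For a variable that differs between modes, adjustment moves the estimate by g times the mean of Δx.

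A negative binomial mixed model with a random intercept, n = 31, unequal exposure per mode and assumed count rates (300 runs) shows this:
- A strong baseline covariate (log slope 0.5) changed the device rate ratio by a median of 0.6%, 95th percentile 2.7%, maximum 5.3%. None of the 300 runs reached 10%.
- A variable shifted by 0.5 SD between modes and carrying half the effect reached 10% in 46% of runs. The rate ratio moved from 0.82 to 0.90.

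**3. When the two rules act.** Assume that 0.2 and 0.38 are on the log-rate scale. The true rate ratio is exp(−0.2) = 0.819, an 18% reduction. A variable carrying share s moves the log rate ratio by 0.2s on average.
- 10% rule: 0.2s = ln(1.10) = 0.095, so s is about 0.48. On average this rule acts only from about half the effect upwards.
- p < 0.05 rule: this acts earlier. With s = 0.25 and a mode shift of 0.25 SD, the slope is 0.25 × 0.2/0.25 = 0.20 and the correlation with the outcome is 0.20/0.38 = 0.53. The p rule selected the variable in 89% of runs and the 10% rule in 14%.

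**4. Effect on power and estimate.** Linear analogue: n = 31, within-subject log rate difference with mean −0.2 and SD 0.38. There is one candidate with SD 1 and an assumed mode shift of 0.25, 0.5 or 1 SD, with both rules applied (4000 runs per cell, Monte Carlo SE at most 0.008). The slope is 0.2s/shift and cannot exceed 0.38. That rules out 50% at 0.25 SD (0.40), and 100% at 0.5 SD (0.40) or less.

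| Share carried | Shift (SD) | Selected | Final-model power | Estimated reduction (true 18%) |
|---|---|---|---|---|
| 10% | 0.25 / 0.5 / 1 | 21 / 10 / 19% | 0.78 / 0.77 / 0.71 | 17 / 17 / 17% |
| 25% | 0.25 / 0.5 / 1 | 88 / 33 / 27% | 0.68 / 0.65 / 0.63 | 14 / 16 / 15% |
| 50% | 0.5 / 1 | 89 / 53% | 0.34 / 0.40 | 10 / 11% |
| 100% | 1 | 96% | 0.08 | under 1% |

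Unadjusted power is 0.81, and Wilcoxon power stays at 0.77–0.80 throughout. The two analyses gave opposite significance verdicts in 17–23% of runs at 25% carried and in 40–46% at 50%.

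Different assumptions (SD 0.6, true rate ratio 0.70, shift 1 SD) give the same pattern. At 25%, 50% and 75% carried, the final model was significant in 54%, 27% and 12% of runs, against 87%, 84% and 81% for the Wilcoxon test. The mean rate ratio moved to 0.76, 0.84 and 0.91.

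**5. Type I error.** No device effect, candidates unrelated to the outcome, 4000 runs:

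| Candidates | Mode shift (SD) | Final model | Either analysis |
|---|---|---|---|
| 4 | 0 / 0.25 / 0.5 | 0.060 / 0.065 / 0.075 | 0.068 / 0.077 / 0.085 |
| 8 | 0 / 0.25 / 0.5 | 0.061 / 0.072 / 0.109 | 0.070 / 0.082 / 0.124 |

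The Wilcoxon test alone gave 0.042–0.052.

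**The case against.** The strongest reply is that the plan can be read as a primary Wilcoxon test followed by a supportive adjusted model. The paired sample size fits that reading, and the screening cannot touch the Wilcoxon test. The harm from adjustment is also conditional: no device-data variable is named, and the other three categories are harmless on the calculation above. A percentage reduction could be computed from the descriptive rates that Section 10.4.2 reports first. Analysts work with modes coded A and B, which limits steering.

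Several details of this stand:
- At small shifts it is mostly the p < 0.05 rule that selects, not the 10% rule.
- At a 1 SD shift, a variable carrying nothing already lowers power to about 0.75 through collinearity, so much of the loss at 10% carried is not a carried effect.
- The 0.08 power and the 0.109 type I error are extreme cells.
- The either-analysis error rate matters only if a claim could rest on either result, which the plan neither makes nor excludes.

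The main point remains. The supportive-model reading conflicts with the text that gives the final model the task of determining the device effect. Nothing limits candidates to variables that mode cannot change. The coding does not help either, since an automatic rule runs equally well on modes A and B.

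**Conclusion.** The concern holds. The missing ranking is plain from the text and needs no assumption. The bias in the final model is a possibility the rules allow, not a certainty: it needs a candidate that varies by mode, is shifted by the warnings and is related to contacts. If such a variable carries a quarter to a half of the effect, final-model power falls from 0.81 to between 0.34 and 0.68, and an 18% reduction is reported as 10–16%. At a tenth carried, the estimate hardly moves. Inflation of type I error is modest in most settings. These sizes rest on reading the plan's inputs as log rates and on assumed shares, shifts and candidate counts. The lasting problem is that the quantity estimated depends on what the screening picks up, with no rule for resolving a disagreement between the two analyses.

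**What to change.** In Section 10.4.2, name one deciding analysis with no data-driven covariate selection, and label the other supportive. Either of these would serve:
- the Wilcoxon signed-rank test, which is closest to the paired basis of Section 10.5; or
- a negative binomial mixed model with device mode, a random subject effect and the pre-specified exposure offset. This has the advantage that test and estimate come from the same model.

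In both cases, take the percentage reduction of Section 4.2.1 from the unscreened model. If the Wilcoxon test is chosen, state that it alone decides significance, so that a differing model interval does not reopen the question.

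If adjustment is wanted, list in advance a few covariates that mode cannot affect. Move the predictor screening to Section 10.4.11 as exploratory, together with any model using variables recorded during home use. The exposure terms are the exception, because they define the rate. Apply the same rules to body contacts in Section 10.4.3.

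The cost is wording in Sections 10.4.2, 10.4.3 and 10.4.11, with no new data, visits or participants. The covariate-adjusted model loses its confirmatory standing.
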